In summary, this study is essential for understanding why patients in Nepal fail to adhere to life-saving medications post-ACS and what can be done to mitigate this problem, ultimately improving patient care and reducing the burden on the healthcare system.

5. Objectives

a. General objectives:

To assess the level of adherence to prescribed secondary prevention medications and identify the factors influencing adherence among patients with Acute Coronary Syndrome (ACS) in Nepal.

b. Specific objectives:

- **To assess the level of adherence to secondary prevention medications (SPMs) among patients discharged after an Acute Coronary Syndrome (ACS) event, including antiplatelets, statins, beta-blockers, and ACE inhibitors/ARBs.**
- **To explore the influence of patient demographic factors** (such as age, gender, education level, occupation, and place of residence) and clinical characteristics (type of ACS, comorbidities) on medication adherence.
- **To identify patient-reported barriers to medication adherence**, including concerns about medication side effects, pill burden, practical issues with medication administration, and difficulties in integrating medications into daily routines.
- **To evaluate the relationship between medication adherence and clinical outcomes**, such as recurrent cardiac events, rehospitalization.

6. Research questions/hypothesis

- What is the level of adherence to secondary prevention medications among Acute Coronary Syndrome (ACS) patients in Nepal, and what demographic, clinical, and patient-reported factors influence this adherence and its associated clinical outcomes?

7. Research design and Methodology

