7.8 Study variables

Dependent Variable:

- **Adherence to Secondary Prevention Medications (SPMs):** This includes adherence levels to specific medications such as antiplatelets, statins, beta-blockers, and ACE inhibitors/ARBs, measured through MYMEDS questionnaire.

Independent Variables:

1. Demographic Factors:

- Age
- Gender
- Education Level
- Occupation
- Place of Residence (Rural vs. Urban)
- Monthly Income

2. Clinical Characteristics:

- Type of Acute Coronary Syndrome (e.g., STEMI, NSTEMI, Unstable Angina)
- Comorbidities (e.g., Hypertension, Diabetes Mellitus, Dyslipidemia, Chronic Kidney Disease)

3. Patient-Reported Factors:

- Concerns about medication side effects
- Pill burden (number of medications)
- Practical issues with medication administration (e.g., difficulties opening bottles)
- Difficulty integrating medications into daily routines

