 - 4. Semi-skilled worker**
 - Factory or workshop laborer, laboratory or library attendant, car cleaner

5. Unskilled worker

- Watchman, peon, domestic servant, rickshaw puller

6. Unemployed

9. **Family Monthly Income (NPR):** _____

- $\geq 97,451$
- 48,751–97,450
- 36,551–48,750
- 24,351–36,550
- 14,551–24,350
- 4,851–14,550
- $\leq 4,850$

10. **Place of Residence:**

- [] Rural
- [] Urban

11. **Distance from Healthcare Facility:** _____ (km)

Section 2: Clinical Information

1. **Type of ACS:**

- [] ST-Elevation Myocardial Infarction (STEMI)
- [] Non-ST-Elevation Myocardial Infarction (NSTEMI)
- [] Unstable Angina

2. **Date of ACS Diagnosis:** _____

3. **Treatment Received:**

- [] Percutaneous Coronary Intervention (PCI)
- [] Coronary Artery Bypass Grafting (CABG)
- [] Medical Management Only

4. **Comorbidities:**

- [] Hypertension
- [] Diabetes Mellitus
- [] Dyslipidemia
- [] Chronic Kidney Disease
- [] Stroke
- [] Peripheral Arterial Disease
- [] Others (Specify): _____

Section 3: Assessment of Adherence**MYMEDS Questionnaire****Section 1: Current Medicines**

Serial Number	Name of Medicines	Administration Time (Morning/Afternoon/Evening/Night)	Reason for Taking Medicine
1	Antiplatelets	_____	_____
2	Statins	_____	_____
3	Beta-blockers	_____	_____
4	ACE inhibitors/ARBs	_____	_____
5	Others (Loop diuretics, Nitrates, specify)	_____	_____

Section Number	Statement	Strongly agree	Agree	Disagree	Strongly disagree
Section 2: Understanding and satisfaction with medicines	a. I fully understand my heart medicines and why they were prescribed.				
	b. My heart medicines seem to be working for me.				
	c. I feel convinced of the importance of all my heart medicines.				
	d. At least occasionally, I need to alter my medicines on my own to make them work or meet my expectations.				

Section 3: Concerns about medicines	a. I worry that one or more of my medicines will do me more harm than good.				
	b. I feel concerned about being prescribed too many medicines.				
	c. I sometimes alter my medicines by cutting back or stopping taking them. (e.g. due to feeling worse, getting worried or for any other reason)				
Section 4: Practical issues that may be a barrier to adherence	a. I have difficulties or problems opening the medicine bottles or blister packs and would like a solution or an alternative.				
	b. I have difficulties or problems swallowing my medicine(s) and would like a solution or an alternative.				

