	c. I have difficulties or problems getting my repeat prescriptions and would like help ordering them from my GP or pharmacy.				
	d. I have difficulties or problems reading the label on the medicines bottle or box and would like a solution or alternative.				

Section 5: Fitting medicines into daily routine	a. I sometimes forget to take my heart medicines.				
	b. I am finding it difficult to fit one or more of my heart medicines into my daily routine.				
	c. I feel inconvenienced/bothered about sticking to all my heart medicines.				

Section 6: Adherence to Individual SPMs

For each of your prescribed medicines (SPMs), please indicate how often you have taken them as prescribed in the PAST MONTH:

Medication	All of the Time	Nearly All of the Time	Most of the Time	About Half the Time	Less than Half the Time
Aspirin					
ACE Inhibitor (e.g. Ramipril, Lisinopril,)					
Beta Blocker (e.g. Acebutalol)					
Medication 4 Statin (e.g. Simvastatin)					
ARIIA (e.g. Candesartan)					

Section 4: Clinical Outcomes

1. **Have you experienced any of the following since discharge?** (Check all that apply)
 - Recurrent chest pain
 - Rehospitalization for cardiac issues
 - Stroke
 - Heart failure symptoms
 - No major events
2. **Follow-up with healthcare provider since discharge:**
 - Yes
 - No
 - If Yes, how many visits: _____

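### The heart failure outcome item does not separate new from continuing symptoms, and the undated stroke comorbidity box lets one post-discharge stroke be recorded as both comorbidity and outcome

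*Combined protocol and SAP*

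**What the plan says.** The fourth specific objective (Section 5b) relates adherence to clinical outcomes, "such as recurrent cardiac events, rehospitalization" being the examples named. The data come from Annex 1, Section 4, item 1, which opens with "Have you experienced any of the following since discharge". The boxes beneath it are "Recurrent chest pain", "Rehospitalization for cardiac issues", stroke, "Heart failure symptoms" and an option for no major event.

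The comorbidity list is in Annex 1, Section 2, item 4. It has boxes for hypertension, diabetes, dyslipidemia, chronic kidney disease, stroke and "Peripheral Arterial Disease", plus a write-in line. It has no heart failure box and no statement of the time to which it refers. The form records "Date of ACS Diagnosis" but has no field for the discharge date or for the date of any outcome event.

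Section 7.8 makes comorbidities independent variables, worded as "Comorbidities (e.g., Hypertension, Diabetes Mellitus, Dyslipidemia, Chronic Kidney Disease". Section 8, the analysis section, contains only template prompts, so no rule there separates earlier disease from later events.

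**The concern.** A patient who has been breathless since the index infarction and remains so can truthfully tick the heart failure item. The only other answer open to that patient, if nothing else happened, is that there was no major event, which fits poorly. The tick then enters the analysis as an outcome of the post-discharge period.

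Heart failure already present at discharge cannot result from adherence after discharge, though it may affect that adherence and the number of medicines prescribed. If the two kinds of tick are pooled, the item partly measures baseline severity. The association with adherence may then be diluted or, if baseline heart failure differs between adherence groups, moved in either direction.

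The stroke problem is smaller. A stroke after discharge can be ticked on both lists. If the comorbidity box is then used as a predictor, the same event may stand on both sides of an analysis, and a comorbidity tick cannot be placed before or after the qualifying ACS.

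**Working it through.** The documents state no figure that depends on these items, so there is none to reproduce. The check is first of wording, then an illustration under assumed rates.

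**Wording, item by item**

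| Item | Tied to the time after discharge? | Separable from baseline disease? |
|---|---|---|
| Chest pain (outcome) | Yes, by the stem | Partly: worded as recurrent |
| Rehospitalization (outcome) | Yes, by the stem and by its nature | Yes |
| Stroke (outcome) | Yes, by the stem | Yes, as worded |
| Heart failure symptoms (outcome) | Yes, by the stem | No: continuing symptoms also occur after discharge |
| Stroke (comorbidity) | No time reference | No |
| Heart failure (comorbidity) | No box; write-in line only | Not captured systematically |

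**Illustration for the heart failure item**

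Assumptions, none of them from the documents: heart failure at discharge, *b*, 10% to 30%; new heart failure among the rest, *n*, 5% to 10%; every patient with baseline heart failure ticks the item.

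Share ticking = *b* + (1 − *b*)*n*. Baseline share of ticks = *b* / [*b* + (1 − *b*)*n*].

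- *b* = 0.10, *n* = 0.10: 0.10 / (0.10 + 0.09) = 0.10 / 0.19 = 53%.
- *b* = 0.30, *n* = 0.05: 0.30 / (0.30 + 0.035) = 0.30 / 0.335 = 90%.

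Now let new heart failure be 10% in non-adherent and 5% in adherent patients.

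- True odds ratio: (0.10/0.90) / (0.05/0.95) = 2.11.
- Baseline 20% in both groups: ticks are 0.20 + 0.80 × 0.10 = 0.28 and 0.20 + 0.80 × 0.05 = 0.24. Observed odds ratio: (0.28/0.72) / (0.24/0.76) = 1.23.
- Baseline 15% non-adherent, 25% adherent: ticks are 0.15 + 0.85 × 0.10 = 0.235 and 0.25 + 0.75 × 0.05 = 0.2875. Observed: (0.235/0.765) / (0.2875/0.7125) = 0.76.
- The same imbalance reversed, 25% non-adherent and 15% adherent: ticks are 0.25 + 0.75 × 0.10 = 0.325 and 0.15 + 0.85 × 0.05 = 0.1925. Observed: (0.325/0.675) / (0.1925/0.8075) = 2.02.

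Equal baseline heart failure dilutes the association. Unequal baseline heart failure can move it either way, and the documents do not say which.

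**How many patients this concerns**

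Section 7.6 assumes 92.5% adherence and needs 106 patients. That implies 106 × 0.075 = 7.95, about 8 non-adherent patients. At 10% new heart failure, 8 × 0.10 = 0.8 events are expected among them.

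**The case against.** Four arguments tell against a broad version of this point.

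1. *Stroke is timed as an outcome.* A reader might infer that stroke is untimed on both lists and that an old stroke could be ticked on either. The stem limits every outcome box to the time after discharge, so as worded an old stroke is not an outcome. Only the comorbidity box is undated. Stroke is also not among the comorbidity examples in Section 7.8, though that list is open-ended and the form collects it. This stands.

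2. *The objective is wider than one box.* A reader might infer that the whole fourth objective mixes baseline disease with later events. Its named examples are recurrent cardiac events and rehospitalization, and rehospitalization follows discharge by its nature. This stands: the weakness lies mainly in the heart failure item and in any summary that includes it. Nor does the form state a rule that continuing symptoms count. It fails to exclude them.

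3. *Other sources may help.* The researcher asks the questions in person (Section 7.5), the form has a write-in line, and record review is planned (Section 7.9). The exclusions in Section 7.7 remove some patients with other conditions. These soften the problem without closing it. No instruction tells the interviewer to separate new from old symptoms, nothing directs the record review to baseline heart failure, and heart failure arising from the ACS is not clearly excluded.

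4. *The practical effect is small.* With about 8 non-adherent patients, odds ratios of 2.11 and 1.23 could not be told apart. This stands on the plan's own adherence figure. That figure comes from a different scale, and the rule in Section 7.10, under which any answer short of full adherence for any medicine counts as non-adherence, may give more non-adherent patients. The documents give no rate for it.

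A larger timing problem also remains: adherence is asked for the past month, while outcomes run from discharge. Rewording these items does not repair that.

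**Conclusion.** The point holds in a limited form. As the form stands, heart failure symptoms continuing from the qualifying ACS can be recorded as a post-discharge outcome and cannot be told from new ones. One post-discharge stroke can also be recorded as both comorbidity and outcome. The main adherence estimate is not affected.

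The size of the bias cannot be derived from the documents. The range of 53% to 90% and the fall from 2.11 to 1.23 rest on assumed rates and on every patient with baseline heart failure ticking the item. Treated patients may be symptom-free, so within each scenario the baseline share is an upper bound. A reader might take the value of 0.76 as evidence that the association would reverse. It comes only from setting baseline heart failure higher in adherent patients, which nothing in the documents supports; the opposite imbalance gives 2.02.

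The correction is worth making because it costs almost nothing and removes an avoidable misclassification from a stated objective.

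**What to change.** On the form:

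- Head the comorbidity list *present at or before the qualifying ACS*.
- Add a tick box for heart failure at discharge from the qualifying ACS.
- Reword the outcome as *new or worsened heart failure symptoms since discharge*.

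In Section 8, state that this item will be analysed in patients without baseline heart failure, or adjusted for it. With few non-adherent patients, the restricted analysis is the simpler choice.

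For forms already completed, take baseline heart failure and the timing of any stroke from the planned record review. Under the existing wording, patients with baseline heart failure may tick the item whatever happened later, so restriction will serve better than adjustment there. Where the records do not settle the matter, report the heart failure item separately and descriptively, and leave it out of any event/no-event summary. Recording the discharge date and event dates would help further.

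The cost is a heading, one reworded item and one more question, with no extra patients or procedures. The downside is that fewer heart failure events will be counted, and a restricted analysis uses fewer patients.

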7.3 Study population/Sampling frame

A sample of adult patients (age ≥ 18 years) who have either come to OPD for follow-up or have been readmitted for having cardiac complications months after surviving ACS (including STEMI, NSTEMI, and unstable angina) in Manmohan Cardiothoracic Vascular and Transplant Centre, Nepal will be selected via **convenience sampling**. The total population under study is around 1000.

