7.7 Inclusion and Exclusion criteria

- **Inclusion Criteria:**

1. Patients diagnosed with ACS, including ST-Elevation Myocardial Infarction (STEMI), Non-ST-Elevation Myocardial Infarction (NSTEMI), or Unstable Angina within the last 12 months.
2. Patients aged 18 years and older.
3. Patients willing to participate and provide informed consent for the study.

- **Exclusion Criteria:**

1. Individuals who have not been diagnosed with ACS or those with other acute or chronic conditions that might influence medication adherence unrelated to ACS.
2. Patients with cognitive impairments or mental health issues that prevent them from understanding or responding accurately to the study questionnaires.
3. Patients with severe chronic conditions (e.g., terminal illness, advanced dementia) that may affect their ability to adhere to medication regimens.

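### The objective 4 rehospitalization item does not separate planned from unplanned cardiac admissions, so scheduled admissions can be counted as adverse outcomes, with an effect of unknown size and direction

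*Combined protocol and SAP*

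**What the plan says.** Section 5b, fourth specific objective, sets out to relate adherence to clinical outcomes "such as recurrent cardiac events, rehospitalization". Rehospitalization is not defined further there. Section 13 expects the findings to feed interventions that lower re-hospitalization.

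The outcome is collected in the annexed pro forma, Section 4 (Clinical Outcomes). The question is "Have you experienced any of the following since discharge", and one of the boxes is "Rehospitalization for cardiac issues". The others are recurrent chest pain, stroke, heart failure symptoms and "No major events".

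Section 2 of the pro forma records PCI, CABG or medical management under treatment received. It asks for the date of the ACS diagnosis but not for the date or intent of a procedure.

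Section 7.3 describes the people to be approached as outpatients at follow-up, or patients who "have been readmitted for having cardiac complications months after surviving ACS". The numbered criteria in section 7.7 require ACS ("or Unstable Angina within the last 12 months") and say nothing about the reason for an admission.

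Section 8, which should hold the analysis plan, contains only the template's prompts.

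**The concern.** The list offers an absence of major events as its alternative, so a ticked rehospitalization box reads as something having gone wrong. The words of the box are wider than that: any admission for a heart-related reason fits them, including one arranged in advance for a procedure. Section 7.4 describes a centre with therapeutic and surgical services, and eligibility spans 12 months after the event, so a scheduled cardiac admission in that window is plausible.

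A scheduled admission is not in itself a consequence of missed tablets. If such admissions are pooled with complications, the objective 4 outcome mixes two different things, and the comparison of adherent with non-adherent patients is distorted. The form determines what is collected, so an analyst could not separate the two afterwards from the study data. The adherence estimate itself, on which the sample size is based, is not affected.

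**Working it through.** **1. Can anything in the plan separate the two kinds of admission?**

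| Place | What it offers | Separates planned from unplanned? |
|---|---|---|
| Pro forma Section 4, outcome box | Cardiac cause, since discharge | No: no reason, date or status |
| Pro forma Section 2, treatment received | PCI, CABG or medical only | No: undated, so an index procedure cannot be told from a later one |
| Section 5b, objective 4 | Names rehospitalization | No: unqualified |
| Section 7.9 | Mentions medical record review | No: no form field or rule uses it to classify admissions |
| Section 8 | Template prompts | No: no scoring rule |
| Sections 9 and 10 | Lists biases and limitations | No: this one is not among them |

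**2. Who can be affected?** A ward patient who enters as section 7.3 describes is in hospital for a complication, so the current admission is not a planned one. The exposure is therefore mainly among outpatients, and among ward patients with an earlier admission since discharge.

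**3. What would it do to the association?** The documents give no event rate, planned-admission share, effect size or power for objective 4, so there is no figure of the plan's to reproduce. Everything below is assumed, for illustration only.

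Let r be the risk of an unplanned admission and p the share with a planned one, independent of each other within an adherence group. The box is ticked if either occurs:

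observed risk = 1 − (1 − r)(1 − p)

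Take r = 0.20 in adherent and 0.40 in non-adherent patients, a true risk ratio of 0.40 / 0.20 = 2.0.

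| p, adherent | p, non-adherent | Observed, adherent | Observed, non-adherent | Risk ratio |
|---|---|---|---|---|
| 0.10 | 0.10 | 1 − 0.80 × 0.90 = 0.28 | 1 − 0.60 × 0.90 = 0.46 | 1.64 |
| 0.15 | 0.15 | 1 − 0.80 × 0.85 = 0.32 | 1 − 0.60 × 0.85 = 0.49 | 1.53 |
| 0.30 | 0.30 | 1 − 0.80 × 0.70 = 0.44 | 1 − 0.60 × 0.70 = 0.58 | 1.32 |
| 0.20 | 0.05 | 1 − 0.80 × 0.80 = 0.36 | 1 − 0.60 × 0.95 = 0.43 | 1.19 |
| 0.05 | 0.20 | 1 − 0.80 × 0.95 = 0.24 | 1 − 0.60 × 0.80 = 0.52 | 2.17 |

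Equal shares, or a larger share in adherent patients, attenuate the ratio. A sufficiently larger share in non-adherent patients inflates it. With 5% in the adherent group, the observed ratio exceeds 2.0 once the non-adherent risk passes 2 × 0.24 = 0.48, that is once p exceeds 1 − 0.52 / 0.60 = 0.133.

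**4. Does this depend on the assumed risks?** Take instead 0.25 in adherent and 0.50 in non-adherent patients (odds ratio 3.00), and let f be the planned share among those without an unplanned admission, so observed risk = r + (1 − r)f.

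- f = 0.10 in both: 0.325 and 0.55, odds ratio 2.54.
- f = 0.20 adherent, 0 non-adherent: 0.40 and 0.50, odds ratio 1.50.
- f = 0.05 adherent, 0.20 non-adherent: 0.2875 and 0.60, odds ratio 3.72.

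The pattern is the same: the direction depends on how planned admissions are spread across the adherence groups, and the plan gives no information on that.

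**The case against.** The strongest reply is that planned admissions are nowhere in the documents. No section mentions staged, scheduled or elective procedures, or how common they are. The account of the centre's services describes the hospital, not this sample. The treatment item follows the type and date of the ACS, so it reads most naturally as treatment of the index event. This stands. It means the plan permits the misclassification but does not show that it will occur, or how often.

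A second reply is that the box sits among adverse events and that, under section 7.5, a researcher asks every question and could clarify it. This has some force, but no instruction tells the interviewer how to treat a scheduled stay, and section 7.1 also allows an online survey.

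A third is that objective 4 is the last of four in a descriptive study sized for an adherence proportion, and that section 10 already concedes the cross-sectional limit and confounding. That bears on priority. It does not cover an outcome item whose meaning is open.

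A reader might infer two stronger things. One is that the study will dilute the adherence–rehospitalization association. The documents do not support that: dilution follows from equal shares or a larger share in adherent patients, and the opposite pattern can inflate the association. The other is that the plan holds two conflicting definitions of readmission. Sections 7.3 and 7.5 describe who is approached and do not define an outcome, so the difference in wording is not a contradiction.

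**Conclusion.** The point holds as a gap in the outcome definition. The item does not distinguish planned from unplanned cardiac admissions, and no other field or rule does so, which means a scheduled admission can be counted as an adverse outcome. The size and direction of the effect on objective 4 cannot be determined from the documents. The risk ratios of 1.19 to 2.17 against a true 2.0 rest entirely on assumed event rates and planned shares; they show that the effect can go either way, not what to expect.

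This is a cheap improvement to a named objective, and it is best made before interviews because the form does not otherwise hold the information. It does not make objective 4 interpretable by itself. Readmission is also a route into the study: if the current admission is counted, every ward-route patient has the outcome, and the rate largely reflects the outpatient/ward mix of a convenience sample. That is a separate problem and remains.

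**What to change.** - In pro forma Section 4, reword the item to *Unplanned rehospitalization for a cardiac complication*.
- Add a separate tick, *Planned admission for a scheduled cardiac procedure*, and state that it is not counted as an event.
- In the fourth specific objective, state that only the unplanned item is the rehospitalization outcome.

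The cost is one reworded item, one added tick-box and one phrase. The downside is a slightly lower event count. If interviews have already begun, the reason for admission in completed forms would have to be recovered from the medical records.
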